7.6 Demographic and Other Baseline Characteristics

Patient's characteristics and other baseline data will be summarized for the FAS and reported using statistical methods described above (see section 7.2 General Methodology).

7.7 Treatment Characteristics

The Study Investigator should perform the surgical procedure according to the appropriate standard procedures and practices at his/her institution using BiZact™. Additionally, the following procedures and assessments will be performed:

- Type of admission
- Adverse Events/Serious Adverse Events assessment
- Intra-operative bleeding volume
 - Record volume of any irrigant used
 - Record presence of gastric fluids
 - Record amount of fluid in suction container prior to stomach drainage
- Surgical performance parameters
 - Surgical technique
 - Operation time
 - Device ease of use
 - Dissection assessment
 - Other alternative devices used (if any)
 - Operation time used
 - Side
 - Reason for use
 - Tonsil size measurement (Measured via water displacement)
 - Using a graduated container that has 1mL markings, fill container to half full with water note mL level. Put the first tonsil into the water and record the mL level. The difference equals the volume of the first tonsil. Remove the first tonsil and note

This document is electronically controlled. Printed copies are considered uncontrolled.

Confidential

water level. Put the second tonsil into the water and record how much the water level rises. The difference equals the volume of the second tonsil.

- Concomitant medications - medications used during procedure, used for Averse Events and used for the treatment of pain (including but not limited to analgesics, anti-inflammatories, etc.)

Surgical procedure data will be summarized on the FAS and reported using statistical methods described above (see section 7.2 General Methodology).

This document is electronically controlled. Printed copies are considered uncontrolled.

Confidential

7.8 Interim Analyses

No interim analysis is planned.

7.9 Evaluation of Objectives

7.9.1 Primary objective

The severity of pain will be analyzed at each post-operative assessment: at days 1 through 7, 10 and 14. This pain score will be assessed quantitatively using the VAS scale and qualitatively using the below subgroups:

- No Pain: VAS= 0
- Mild Pain: VAS > 0 and < 4
- Moderate: VAS ≥ 4 and < 7
- Severe: VAS ≥ 7

Friedman's test will be performed so as to assess the distribution of the VAS along the follow-up and testing whether the VAS per visits are from a same population:

- H_0 : $M_1 = M_2 = M_3 = M_4 = M_5 = M_6 = M_7 = M_{10} = M_{14}$ (the distribution of the VAS is the same in all timepoints)
- H_a : There is at least one pair (i,j) such as $M_i \neq M_j$.

Subgroup analyses will be performed according to the use of pain killers.

Primary objective analysis will be run on both FAS and PPAS.

7.9.2 Secondary objectives

- The incidence of patients with analgesic consumption will be assessed at each timepoint and globally using frequency and percentages. On the whole follow-up the total consumption of analgesics (narcotics and non-narcotics analgesics) will be assessed. Patients with analgesics will be identified based on dosing diary.
- Ability to return to normal diet and normal activity and patients quality of life after operation will be presented:
 - Calculating the time (counts, means, standard deviations, medians, minimum and maximum) between the operation and the return to normal diet or activity dates.
 - Calculating the incidence of patients being returned to normal diet or activity after operation.
 - Using the **EORTC QLQ-H&N35 questionnaire**:

The head & neck cancer module is meant for use among a wide range of patients with head & neck cancer, varying in disease stage and treatment modality (i.e. surgery, radiotherapy and chemotherapy) (Bjordal and Kaasa, 1992; Bjordal et al., 1994, 1999, 2000) (1-3). The module comprises 35 questions assessing symptoms and side effects of treatment, social function and body image/sexuality. The module has been

This document is electronically controlled. Printed copies are considered uncontrolled.

Confidential

developed according to the guidelines, and pretested on patients from Norway, Sweden, Denmark, the UK and French-speaking Belgium. It has been field tested in Norway, Sweden and The Netherlands, and in a large cross-cultural study involving more than ten countries (EORTC Protocol 15941).

Scoring of the head & neck cancer module

The head & neck cancer module incorporates seven multi-item scales that assess pain, swallowing, senses (taste and smell), speech, social eating, social contact and sexuality. There are also eleven single items. **For all items and scales, high scores indicate more problems** (i.e. there are no function scales in which high scores would mean better functioning).

Friedman's test will be applied to assess the distribution of the scores along the follow-up timepoint:

- $H_0: M_1 = M_2 = M_3 = M_4 = M_5 = M_6 = M_7 = M_{10} = M_{14}$ (The distribution of the Symptom score is the same in all timepoints)
- H_a : There is at least one pair (i,j) such as $M_i \neq M_j$.

Scale name	Scale	Number of items	Item range*	QLQ-H&N35 Item numbers
Symptom scales / items				
Pain	HNPA	4	3	1-4
Swallowing	HNSW	4	3	5-8
Senses problems	HNSE	2	3	13, 14
Speech problems	HNSP	3	3	16, 23, 24
Trouble with social eating	HNSO	4	3	19-22
Trouble with social contact	HNSC	5	3	18, 25-28
Less sexuality	HNSX	2	3	29,30
Teeth	HNTE	1	3	9
Opening mouth	HNOM	1	3	10
Dry mouth	HNDR	1	3	11
Sticky saliva	HNSS	1	3	12
Coughing	HNCO	1	3	15
Felt ill	HNFI	1	3	17
Pain killers	HNPk	1	1	31
Nutritional supplements	HNNu	1	1	32
Feeding tube	HNFE	1	1	33
Weight loss	HNWL	1	1	34
Weight gain	HNWG	1	1	35

* Item range is the difference between the possible maximum and the minimum response to individual items.

Example:

Pain

$$\text{RawScore} = (Q1 + Q2 + Q3 + Q4)/4$$

$$\text{Pain Score} = \{(\text{RawScore}-1)/\text{Item range}\} * 100$$

Questions scores

Not at all = 1

No = 1

A little = 2

Yes = 2

Quite a bit = 3

Very much = 4

This document is electronically controlled. Printed copies are considered uncontrolled.

Confidential

- The incidence of patients having a post-operative hemorrhage, primary and secondary bleeding, and post-operative readmission along the follow-up will be assessed.
- Intra-operative bleeding, irrigant volumes and operative time will be calculated (counts, means, standard deviations, medians, minimum and maximum).

Secondary objectives will be run on both FAS and PPAS.

This document is electronically controlled. Printed copies are considered uncontrolled.

Confidential

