5.2.2. Secondary Endpoint(s)

- Analgesic consumption
- Ability to return to normal diet (days 1-7, 10, 14)
- Ability to return to normal activity (days 1-7, 10, 14)
- Incidence of post-operative hemorrhage
- Primary (≤ 24 hrs) bleeding and
- Secondary (>24 hrs) bleeding
- Incidence of post-operative readmission
- Intra-operative bleeding volume- volume of stomach juices and blood should be measured prior to stomach draining
- Irrigant volume – volume to be recorded of operative field irrigant used during procedure
- Operative time - time from the first incision to complete hemostasis of the tonsillar bed

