9.2. Prior and Concomitant Medications

All concomitant medications will be managed by the investigator per their standard of care and will be recorded on the appropriate eCRFs from Screening/Baseline through end of study.

Consumption of recommended standard of care analgesic pain regimen post-procedure is as follows;

- 10 mg dose dexamethasone intra-operative
- Ibuprofen 800 mg q8hrs
- Hydrocodone/acetaminophen 10/325 mg q4 hrs PRN
- Any modifications to recommended pain regimen will be noted in the eCRF

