9.5. Medication Compliance

A recommended standard of care analgesic pain regimen is listed in section (9.2). Compliance to this regimen will be monitored via the at home survey (EORTC QLQ – H&N35, Appendix A).

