17.1.1. EORTC QLQ-H&N35 (English)

ENGLISH

EORTC QLQ - H&N35

Patients sometimes report that they have the following symptoms or problems. Please indicate the extent to which you have experienced these symptoms or problems during the past week. Please answer by circling the number that best applies to you.

During the past week:		Not at all	A little	Quite a bit	Very much
31.	Have you had pain in your mouth?	1	2	3	4
32.	Have you had pain in your jaw?	1	2	3	4
33.	Have you had soreness in your mouth?	1	2	3	4
34.	Have you had a painful throat?	1	2	3	4
35.	Have you had problems swallowing liquids?	1	2	3	4
36.	Have you had problems swallowing pureed food?	1	2	3	4
37.	Have you had problems swallowing solid food?	1	2	3	4
38.	Have you choked when swallowing?	1	2	3	4
39.	Have you had problems with your teeth?	1	2	3	4
40.	Have you had problems opening your mouth wide?	1	2	3	4
41.	Have you had a dry mouth?	1	2	3	4
42.	Have you had sticky saliva?	1	2	3	4
43.	Have you had problems with your sense of smell?	1	2	3	4
44.	Have you had problems with your sense of taste?	1	2	3	4
45.	Have you coughed?	1	2	3	4
46.	Have you been hoarse?	1	2	3	4
47.	Have you felt ill?	1	2	3	4
48.	Has your appearance bothered you?	1	2	3	4

Please go on to the next page

ENGLISH

During the past week:	Not at all	A little	Quite a bit	Very much
49. Have you had trouble eating?	1	2	3	4
50. Have you had trouble eating in front of your family?	1	2	3	4
51. Have you had trouble eating in front of other people?	1	2	3	4
52. Have you had trouble enjoying your meals?	1	2	3	4
53. Have you had trouble talking to other people?	1	2	3	4
54. Have you had trouble talking on the telephone?	1	2	3	4
55. Have you had trouble having social contact with your family?	1	2	3	4
56. Have you had trouble having social contact with friends?	1	2	3	4
57. Have you had trouble going out in public?	1	2	3	4
58. Have you had trouble having physical contact with family or friends?	1	2	3	4
59. Have you felt less interest in sex?	1	2	3	4
60. Have you felt less sexual enjoyment?	1	2	3	4

During the past week:	No	Yes
61. Have you used pain-killers?	1	2
62. Have you taken any nutritional supplements (excluding vitamins)?	1	2
63. Have you used a feeding tube?	1	2
64. Have you lost weight?	1	2
65. Have you gained weight?	1	2

|

© Copyright QLQ-H&N35 1994, EORTC Quality of Life Group, version 1. All rights reserved

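### The protocol takes analgesic consumption from a past-week yes/no item, the SAP takes it from a diary the protocol does not contain, and the daily incidence pools all analgesics

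*Combined protocol and SAP*

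**What the plan says.** CIP 5.2.2 lists "Analgesic consumption" as a secondary endpoint, with no unit, drug class or time frame. The synopsis puts it among the items on a form that the subject completes on days 1–7, 10 and 14.

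CIP 9.2 gives the regimen as a recommendation: "Consumption of recommended standard of care analgesic pain regimen post-procedure is as follows". One analgesic line has a fixed interval, "Ibuprofen 800 mg q8hrs". The hydrocodone/acetaminophen line is as needed (PRN). No duration is given, and modifications are noted in the eCRF.

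On the source, CIP 9.1.4 lists consumption of the regimen among the items collected on the at-home QLQ-H&N35. CIP 9.5 says: "Compliance to this regimen will be monitored via the at home survey (EORTC QLQ – H&N35, Appendix A". On that form (CIP 17.1.1) the only analgesic question is item 61, "Have you used pain-killers", answered No or Yes for the past week.

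SAP 7.9.2 plans two summaries: "The incidence of patients with analgesic consumption will be assessed at each timepoint and globally using frequency and percentages", and "On the whole follow-up the total consumption of analgesics (narcotics and non-narcotics analgesics) will be assessed". Its source is different: "Patients with analgesics will be identified based on dosing diary". SAP 7.12 says the analysis corresponds to the one planned in the CIP.

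**The concern.** There are two problems of unequal strength.

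The firmer one is the source. The instrument the CIP names cannot yield what the SAP tabulates, and the instrument the SAP names is not in the CIP's Table 1, procedures or appendices. Sites therefore have no instruction in the CIP to issue or collect a diary. Daily as-needed doses that were not written down at the time cannot be rebuilt reliably at the day 14 visit.

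The second is the measure. The per-timepoint incidence counts any analgesic. A subject who follows the fixed-interval line is a consumer on every day it runs, whatever the pain, so changes in as-needed use can be masked.

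Both bear on the primary endpoint. With no comparator, same-day analgesic use is essential context for the VAS, and SAP 7.9.1 plans VAS subgroups by pain-killer use without defining that use.

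**Working it through.** The documents give no figure for this endpoint, so there is none to reproduce. The check has three steps.

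**1. What is needed against what each source holds.**

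| Needed | QLQ-H&N35 item 61 (CIP 9.1.4, 9.5) | Dosing diary (SAP 7.9.2) |
|---|---|---|
| Use at each timepoint | No: past-week recall | Not described in the CIP |
| Total consumption | No: no drug, dose or count | Not described in the CIP |
| Compliance with the regimen | No: does not identify the drug | Not mentioned in CIP 9.5 |

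The daily VAS sheet (CIP Appendix B) carries a mark, a date and a time, and no medication field. At day 14 the subject returns only the VAS and QoL forms (CIP Table 1 and 9.1.4).

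**2. How far a past-week answer departs from daily use.** The timepoints t are days 1–7, 10 and 14, nine in all. Suppose a subject takes analgesics every day up to a last day L. True same-day use holds when t ≤ L. The past-week answer is Yes when t − 6 ≤ L, or when t − 7 ≤ L if the week is counted as seven days back.

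| L | True use | Yes (t − 6) | Yes (t − 7) |
|---|---|---|---|
| 1 | 1 of 9 | 7 of 9 | 7 of 9 |
| 3 | 3 of 9 | 7 of 9 | 8 of 9 |
| 5 | 5 of 9 | 8 of 9 | 8 of 9 |
| 7 | 7 of 9 | 8 of 9 | 9 of 9 |

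This shows what item 61 would give if it were used. The SAP does not say it will be the source for this endpoint.

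**3. Dilution in the pooled daily incidence.** Let a be the share taking the fixed-interval drug on a given day and p the share taking the as-needed drug. Both are assumed, and they are treated as independent.

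Any-use = a + (1 − a)p. When p falls from 0.90 to 0.10, any-use falls by (1 − a) × 0.80.

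| a (assumed) | Any-use at p = 90% | Any-use at p = 10% | Fall in points |
|---|---|---|---|
| 50% | 95% | 55% | 40 |
| 80% | 98% | 82% | 16 |
| 90% | 99% | 91% | 8 |
| 100% | 100% | 100% | 0 |

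The as-needed share falls by 80 points in every row. For the subgroups in SAP 7.9.1, with 48 subjects and a = 90–100%, at most 48 × 0.10 = 4.8 subjects, so about 0 to 5, could be non-users on a given day.

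**The case against.** The best defence is that the SAP does not use item 61 to identify analgesic users. It names a diary. The CIP also requires concomitant medications on eCRFs through end of study, and SAP 7.7 includes drugs given for pain. The list in CIP 9.1.4 is loosely drafted: it puts readmission and the day 14 clinic visit under the same home survey. The synopsis shows that recording by the subject on each day was intended. The eCRF is not among the documents and the table shells are in a separate file, so some of the missing detail may exist there.

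Much of this stands. A reader might infer that the endpoint rests on item 61 alone, and the documents do not support that. But a diary that the CIP neither schedules nor appends is still an unreconciled source, and CIP 9.5 still assigns compliance to a form that cannot show it. No home record of daily doses is described behind the concomitant-medication row.

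A reader might also infer that the daily incidence is flat by design and reflects the regimen rather than need. That is not shown. The regimen is only recommended, can be modified and has no stated duration. At 50% use of the fixed-interval drug, any-use would still move by 40 points, and on days 10 and 14 it may partly reflect need. Nor is the endpoint only any-use: a whole-follow-up total naming narcotics and non-narcotics is planned. Any-use is a legitimate descriptive summary in a pilot without a powered hypothesis. Finally, as-needed should not be equated with narcotic, because investigators manage concomitant drugs by their own standard of care.

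**Conclusion.** The point holds in two parts.

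The source conflict needs no assumption. The CIP names an instrument that cannot measure daily use, total consumption or compliance, and the SAP names one that the CIP lacks. SAP 7.12's statement that the analysis matches the CIP is therefore not accurate here.

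The dilution is conditional. It costs most of the signal if 80–100% of subjects take the fixed-interval drug (a fall of 16 to 0 points against 80 in as-needed use) and less at 50% (40 points). Adherence and duration are not in the documents, so the actual size is unknown. What is certain is that the daily summary has no planned split by class, the total has no unit, and the pain-killer subgroups have no definition.

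This should be put right, mainly because daily doses not recorded at the time are hard to recover.

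**What to change.** **CIP.** Name one source for analgesic consumption and compliance. The simplest is to add two fields to the daily VAS sheet: the number of narcotic doses and of non-narcotic doses in the last 24 hours. Alternatively, append the diary. Cite the chosen form in Table 1, 9.1.4 and 9.5 in place of the QLQ-H&N35.

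**SAP 7.9.2.** Name the same source. Keep the any-use incidence, and add narcotic and non-narcotic use separately at each timepoint (percent of subjects and number of doses) beside the same day's VAS. State the unit of the total.

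**SAP 7.9.1.** Use the same definition for the pain-killer subgroups.

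The cost is two count fields on an existing sheet and in the eCRF, short edits to the SAP, and slightly more subject burden. No change to the regimen is proposed.

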8.2. Subject Enrollment

After being informed of the nature of the study, the subject will provide written informed consent that has been approved by the sponsor and the appropriate IRB/EC of the respective clinical site. A minimum of 48 subjects will be enrolled in the study at up to 3 sites with competitive enrollment not to exceed 24 subjects per site. Subjects' participation in the study will last 14 days (+3) post procedure.

A subject is considered enrolled in the study when ICF is signed, and must be followed for the full 14 days follow-up regardless of whether or not the subject received treatment with the study device.

The procedure will be performed per the institution's standard practice. Subjects will be considered for the study if they meet specific preoperative and intraoperative inclusion/exclusion criteria. The criteria for enrollment must be followed explicitly.

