4.2. Secondary objectives

Several secondary hypotheses will be analyzed:

- To assess the incidence of patients with post-operative analgesic consumption
- To assess the ability to return to normal diet and normal activity after operation:
 - Time between dates of operation and return to a normal situation
 - Incidence of patients returning to a normal situation

- To assess the incidence of patients with of post-operative hemorrhage
 - Incidence of patients with primary bleeding, occurring at the latest 24 hours after operation.
 - Incidence of patients with secondary bleeding, occurring more than 24 hours after operation.

- To assess the incidence of patients with post-operative readmission

- To assess the quantity of intra-operative bleeding volume

- To assess the quantity of intra-operative irrigant volume

- To assess the operative time from the first incision to complete hemostasis of the tonsillar bed (procedure duration and device use duration)

This document is electronically controlled. Printed copies are considered uncontrolled.

Confidential

5. Investigation Plan

This is a Prospective, multi-center, single-arm non-comparative pilot study to assess the severity of post-operative pain with the use of BiZact™ for tonsillectomy.

A minimum of 48 subjects being treated with BiZact™ for tonsillectomy may be enrolled at up to 3 sites in the United States and Europe with competitive enrollment not to exceed 24 subjects per site.

Subjects' participation in the study will last 14 days 14 (+3) post-procedure. Assessments of pain, quality of life, safety, readmission, concomitant medications, ability to return to normal diet and activity will be performed. An at home survey form during post-operative days 1 through 7 and day 10 will be used. At day 14 (+3) these parameters will be evaluated via a clinical follow-up visit in the sites.

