7.4 Handling of Missing Data and Dropouts

No method of imputation will be used for missing data. A summary of missing data will be provided according to the number of subjects, the time points where the data are missing and clinical center. For each clinical center, number and percent of subjects with no missing data will be presented in tabular form.

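### SAP 7.9.2 gives no rule, when summarising time to return to normal diet and activity, for subjects not back to normal at last contact (day 14 +3)

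*Combined protocol and SAP*

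**What the plan says.** SAP 4.2 lists, under return to normal diet and activity, "Time between dates of operation and return to a normal situation" and the incidence of return. SAP 7.9.2 turns these into two summaries, to be run on both the FAS and the PPAS:

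- Time: "Calculating the time (counts, means, standard deviations, medians, minimum and maximum) between the operation and the return to normal diet or activity dates".
- Incidence: "Calculating the incidence of patients being returned to normal diet or activity after operation".

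The SAP is printed twice in the file, and these bullets are the same in both copies.

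On follow-up, protocol 8.2 says that "participation in the study will last 14 days (+3) post procedure". Protocol 5.2.2 ties the endpoint to scheduled days, "Ability to return to normal diet (days 1-7, 10, 14", and does the same for activity. SAP section 5 adds, for the last of these days, "At day 14 (+3) these parameters will be evaluated via a clinical follow-up visit in the sites".

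On absent data, SAP 7.4 says "No method of imputation will be used for missing data", and protocol 13.6 agrees. SAP 7.4 also promises that "A summary of missing data will be provided according to the number of subjects", time point and center. Protocol 13.4.2 does not mention return to diet or activity. Neither text gives a censoring rule, a Kaplan-Meier summary or an assigned value for a subject without a return date. SAP Appendix 1 (the table shells) is a separate file and was not available.

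**The concern.** Time to return is a time-to-event quantity observed for about two weeks. For a subject still not back to normal at the last visit, all that is known is that the time exceeds follow-up. A mean or median of observed date differences cannot use that information. Unless a rule says otherwise, the subject is left out and the summary becomes conditional on having recovered in time.

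Faster return to normal diet and activity is one of the potential benefits named in protocol 10.2, and protocol 4.2 foresees offering the results for publication. A mean computed only from those who recovered could be quoted as the recovery time of all treated adults.

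**Working it through.** The plan states no expected recovery time, so there is no figure to reproduce. Two questions can be checked: which way the omission moves the result, and by how much under stated assumptions.

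**Inputs from the documents.** Time is return date minus operation date (SAP 4.2, 7.9.2). Last contact is day 14 to 17 (protocol 8.2). There is no imputation (SAP 7.4). The minimum sample is 48 (protocol 13.2). **Assumed:** the share p not returned and the shape of the recovery-time distribution.

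**Case 1: true return dates recorded.** Let m be the mean among returners and u the true mean among those not returned, each followed to at least day 14, so u > 14. Then

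true mean − printed mean = [(1 − p)m + pu] − m = p(u − m) > p(14 − m).

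With an assumed printed mean of 8 days, the bound is p × 6: 0.05 × 6 = 0.3, 0.10 × 6 = 0.6 and 0.20 × 6 = 1.2 days. With a common last contact, every omitted value exceeds every retained one. Omitting them therefore lowers the mean and cannot raise the median.

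Simulation: n = 48, whole-day dates, cut-off day 14 or 17, Weibull shapes 1.5, 2 and 3 and lognormal log-SD 0.4, 0.5 and 0.6, samples with at least one subject not returned. The table gives ranges of the average shortfall in days.

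| Share not returned | Bound on mean (m = 8) | Mean too short by | Median too short by | Samples with median unchanged |
|---|---|---|---|---|
| 5% | > 0.3 | 0.4–0.9 | 0.2–0.3 | 52–68% |
| 10% | > 0.6 | 0.7–1.6 | 0.4–0.7 | 27–47% |
| 20% | > 1.2 | 1.4–3.1 | 1.0–1.8 | 5–17% |

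An illustration with invented data: of 48 subjects, 41 return on days 5 to 14, with times summing to 363, so the printed mean is 363/41 = 8.85 and the median 9. Seven do not return. Placing them at day 15, the earliest possible whole day, gives (363 + 7 × 15)/48 = 468/48 = 9.75, with the median still 9.

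**Case 2: only scheduled status recorded.** A return on day 8 or 9 is then first seen on day 10, and one on days 11 to 13 is first seen on day 14. This lateness works against the omission. Weibull times, n = 48, cut-off day 14, ranges over repeated runs:

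- Shape 3, 10% not returned: printed mean 10.2–10.3 against a true 9.5, median 10.1–10.2 against 9.4. Both are too long.
- Shape 1.5, 20% not returned: printed mean 7.8–7.9 against 9.2, median 7.5–7.6 against 8.0. Both are too short.

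The sign is therefore not determined.

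**Case 3: loss before day 14.** The unseen time may be short or long, so the direction is again open.

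**Which case applies?** SAP 7.9.2 speaks of dates, but neither document names the field that holds them. The printed QLQ-H&N35 has no item on normal diet, normal activity or a return date. The day-14 visit could supply one. The SAP also refers to a dosing diary that is not among the printed appendices, so other unprinted forms may exist.

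**The case against.** The strongest reply is that the plan already reports the result in two parts: the time among those who returned, and the proportion who returned. With the counts and the SAP 7.4 missing-data summary, a reader can see how many are left out. That stands as mitigation. It does not make the mean or median describe all treated subjects.

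Second, the exclusion is inferred. SAP 7.4 bars imputing missing data, but a subject seen at day 14 and known not to have returned has an observed status, so 7.4 does not strictly settle the handling. The unseen table shells could contain a rule. Both points are fair. What remains is that the SAP text has no rule, and a date difference cannot be computed without a date.

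Third, a reader might infer that the printed mean and median must be too short whenever someone has not returned. The documents do not support that. It fails for status-only data and is open for early losses. Even with true dates and last contact varying over days 14 to 17 there is a contrived exception: 47 subjects return on day 16, and one, last seen on day 14, returns on day 15. Omitting that one raises the mean from (47 × 16 + 15)/48 = 15.98 to 16.00. It needs returners averaging beyond day 14, and it arose in no simulated trial.

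Fourth, the study is single-arm, descriptive and has no powered hypothesis. That limits the weight of the point.

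**Conclusion.** The concern holds in a limited form. As written, and subject to the table shells, the SAP's time-to-return summary covers only subjects who recovered within follow-up. With recorded dates and a common last contact, the mean is too short and the median too short or unchanged; otherwise the direction is not determined. The size rests wholly on an assumed share not returned and an assumed distribution, and it is zero if everyone returns. At 5%, the average median shift is only 0.2 to 0.3 day, and the median is unchanged in more than half of samples.

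The importance is minor to moderate. One descriptive secondary result is affected. The primary pain analysis is untouched, and nothing here supports reading the point as a threat to the main conclusion.

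**What to change.** Replace the time bullet in SAP 7.9.2, in both printed copies, with wording such as:

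*Time from operation to first return to normal diet, and separately to normal activity, will be estimated by Kaplan-Meier in all FAS subjects and repeated in the PPAS. Subjects who have not returned are censored at their last completed assessment. The median with 95% CI (if reached) and the cumulative percent returned at days 7, 10 and 14 will be reported.*

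The SAP should also name the field used. If only scheduled status is recorded, use an interval-censored (Turnbull) estimate or report only the cumulative percent returned at each assessment day.

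The distinction matters. With 20% not returned and Weibull shapes 2 / 3, the true medians are 9.19 / 10.57. From exact dates, Kaplan-Meier gives 9.06 / 10.47, against 7.88 / 9.53 for returners only. From scheduled status, Kaplan-Meier treated as exact gives 10.57 / 12.97, while Turnbull gives 9.24 / 10.59.

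The cost is SAP wording and slightly more analysis work if a date or status field exists. If neither exists, adding one may need an amendment under protocol 15.6. The median may not be estimable if fewer than half return; the cumulative percents can still be reported.
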